9.5.3 Transcriptome Analyses

We will measure the host and viral transcriptome pre- and post-dosing by performing RNA sequencing (RNA-seq) on isolated CD4+ T-cells and applying validated bioinformatic pipelines for gene expression analysis. Transcriptomic profiling of longitudinal samples will enable characterization of the effects of kansui (which contains ingenols) on host gene expression. In addition, consideration of the gene expression data within the context of the aforementioned virologic measurements will allow us to identify specific host transcriptomic correlates of viral reactivation. We hypothesize that the expression of particular genes (NFkB pathway components, cell-cycle regulators, cell-intrinsic immune factors) will be associated with the degree of viral reactivation.

9.6 Optional Tissue Banking

We are interested in collecting plasma and peripheral blood mononuclear cells taken from peripheral whole blood to be used in future studies on HIV eradication, including immunologic studies to evaluate markers of inflammation and viral transcription. Provided samples will be shipped from the University of Utah to be stored and maintained as part of the UCSF SCOPE Cohort at the UCSF AIDS Specimen Bank (ASB), which specializes in biospecimen storage and processing. Specimens will be stored in Oyster Point at [name].

Specimens stored for future use will not contain any identifiable information. Samples will be coded with a 4-digit PID code and include the collection date and specimen type (i.e., PBMC, plasma, serum, etc.). This code will be kept confidential and only the Principle Investigators will have access to the key linking specimens to study participants. The Principle Investigator will not give participant names or other identifying information to researchers who want to use specimens stored in the tissue bank, but will only provide non-identifying information, like age and disease history.

Future studies may be performed by scientists based at the University of Utah, the University of California, San Francisco and/or by scientists based at other institutions, such as other universities, the NIH and commercial laboratories. The types of studies which may be performed using tissue bank specimens include:

- tests for infections that are common in HIV-infected patients, such as cytomegalovirus or human herpesvirus 8
- genetic testing
- new tests to measure the amount of “latent” HIV reservoir.

Genetic information (genotype data) and medical record data (phenotype data) may be shared broadly in a coded form for future genetic research or analysis. Non-identifiable medical information (diagnoses, blood pressure, age if less than 85) may be provided to other scientists or companies not at the University of Utah or UCSF, including a public government health research database. Research results from studies conducted from the

tissue bank will not be returned to participants, included in patient medical records, or provided to their local study doctors.

Researchers that wish to obtain tissue samples from the bank are required to complete a SCOPE sample request form, which is reviewed and approved by the SCOPE study PI, [name], MD, and the primary study coordinator, [name]. [name] is a Professor of Medicine in Residence at the University of California, San Francisco (UCSF) and a faculty member in the Division of HIV, Infectious Diseases and Global Medicine at Zuckerberg San Francisco General Hospital. [name] has been engaged in HIV research and clinical care since 1993.

Specimens will be kept until they are used up or destroyed.

Providing the specimen for use in future research is optional for participants. Should a participant choose to withdraw their sample from the tissue bank they can have their blood sample removed by contacting the Principle Investigator using contact information contained in the consent and authorization form.

10 ADVERSE EXPERIENCE REPORTING AND DOCUMENTATION

10.1 Adverse Events

An adverse event (AE) is any untoward medical occurrence in a clinical investigation of a patient administered a pharmaceutical product and that does not necessarily have a causal relationship with the treatment. An AE is therefore any unfavorable and unintended sign (including an abnormal laboratory finding), symptom or disease temporally associated with the administration of an investigational product, whether or not related to that investigational product. An unexpected AE is one of a type not identified in nature, severity, or frequency in the current Investigator's Brochure or of greater severity or frequency than expected based on the information in the Investigator's Brochure.

The Investigator will probe, via discussion with the participant, for the occurrence of AEs during each participant visit and record the information in the site's source documents. Adverse events will be recorded in the patient CRF. Adverse events will be described by duration (start and stop dates and times), severity, outcome, treatment and relation to study drug, or if unrelated, the cause.

AE Severity

The National Cancer Institute's Common Terminology Criteria for Adverse Events (CTCAE) Version 3.0 should be used to assess and grade AE severity, including laboratory abnormalities judged to be clinically significant. The modified criteria can be found in the study manual. If the experience is not covered in the modified criteria, the guidelines shown in Table 1 below should be used to grade severity. It should be pointed out that the term "severe" is a measure of intensity and that a severe AE is not necessarily serious.

Table 1. AE Severity Grading

Severity (Toxicity Grade)	Description
Mild (1)	Transient or mild discomfort; no limitation in activity; no medical intervention or therapy required. The participant may be aware of the sign or symptom but tolerates it reasonably well.
Moderate (2)	Mild to moderate limitation in activity, no or minimal medical intervention/therapy required.
Severe (3)	Marked limitation in activity, medical intervention/therapy required, hospitalizations possible.
Life-threatening (4)	The participant is at risk of death due to the adverse experience as it occurred. This does not refer to an experience that hypothetically might have caused death if it were more severe.

AE Relationship to Study Drug

The relationship of an AE to the study drug should be assessed using the following the guidelines in Table 2.

Table 2. AE Relationship to Study Drug

Relationship to Drug	Comment
Definitely	Previously known toxicity of agent; or an event that follows a reasonable temporal sequence from administration of the drug; that follows a known or expected response pattern to the suspected drug; that is confirmed by stopping or reducing the dosage of the drug; and that is not explained by any other reasonable hypothesis.
Probably	An event that follows a reasonable temporal sequence from administration of the drug; that follows a known or expected response pattern to the suspected drug; that is confirmed by stopping or reducing the dosage of the drug; and that is unlikely to be explained by the known characteristics of the participant's clinical state or by other interventions.
Possibly	An event that follows a reasonable temporal sequence from administration of the drug; that follows a known or expected response pattern to that suspected drug; but that could readily have been produced by a number of other factors.
Unrelated	An event that can be determined with certainty to have no relationship to the study drug.

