PRIMARY ENDPOINT	
 • Safety and tolerability of 1 g of Euphorbia kansui extract powder, prepared as tea, given as a single or 3 consecutive daily doses; no Grade 2 or greater clinical or laboratory adverse effects
SECONDARY ENDPOINTS	
 • Immunologic effect on CD4+ and CD8+ T cell activation (CD69, CD38, and HLA-DR expression on CD4+ and CD8+ T cells measured by flow cytometry). • Virologic effect on latent HIV Reservoir (cell-associated HIV RNA and plasma HIV RNA measured by rtPCR).
OTHER EVALUATIONS	With colleagues from the University of Utah Department of Pharmacology and Toxicology, the study team has begun developing an assay to measure levels of ingenol in participant plasma samples. Based on the bioassays performed in [name]'s lab at UCSF, the abundance of ingenol in Euphorbia kansui extract powder is estimated to be approximately 1:100. We will be storing plasma samples collected from this study in order to measure plasma ingenol levels post-dosing with kansui as part of later pharmacokinetic/pharmacodynamics analyses.
SAFETY EVALUATIONS	
Incidence of adverse events
 
Interim analysis following completion of Cohort 1

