10.4 Criteria for Discontinuation

Safety will be monitored by the dedicated SMC, led by a qualified HIV specialist in the University of Utah Department of Medicine (see Section 13 below). The SMC will have full and final authority to stop the study at any point for safety concerns. Given the unknown safety profile of *Euphorbia kansui*, the first participant in each dosing level will complete 5 days of study prior to any further participants commencing the study. The decision to proceed with further drug administration will be taken by the Principal Investigator, taking into consideration clinical and laboratory adverse events. The decision to proceed with the next dosing level will be taken by the SMC. Specifically, dosing will be paused and the SMC will be consulted if one Grade 4 or two Grade 3 drug related adverse events or laboratory abnormalities are reported.

In addition, since there is currently insufficient data demonstrating the effect of kansui on antiretroviral therapy or other concomitant medications (and vice versa), we will evaluate serum HIV-1 RNA levels using standard clinical assays within each dosing cohort prior to dose escalation. HIV RNA measures will be collected on the initial dosing day(s) (Day 1 for Cohort 1, Days 1-3 and 102-104 for Cohort 2), at the 24-hour post dosing follow-up visits on Day 2 (for Cohort 1) and Days 4 and 105 (for Cohort 2), and on Day 31 and 132. This is to safeguard against the potential risk of virologic failure and/or the development of resistance due to sub-therapeutic antiretroviral therapy drug levels in study participants.

Specifically, safety discontinuation criteria will include:

1. Any serious adverse event assessed as at least possibly related to study treatment:
 - a. Any Grade 4 drug-related adverse event or laboratory abnormality
 - b. Two Grade 3 drug-related adverse event or laboratory abnormality
2. Virologic failure (defined as any two consecutive HIV-1 RNA levels >200 copies/mL or a single HIV-1 RNA level >1000 copies/mL). These values would be above the levels predicted to be seen with HIV reactivation with most current latent reactivating agents and are safety stopping criteria currently used for other HIV latent reactivating agent trials, e.g., the AIDS Clinical Trials Group (ACTG 5336) trial, evaluating the role of Sirolimus on immune activation and the latent reservoir in chronic HIV-infected, ART-suppressed individuals.
3. Pregnancy or breastfeeding

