14.3 Analysis of Primary Endpoint

The safety and tolerability data will be summarized by dosing cohort. Adverse events will be tabulated by dosing cohort and will include the number of participants for whom the event occurred, the rate of occurrence, and the severity and relationship to study drug. We may be underpowered to perform Fisher's exact tests to compare crude rates of adverse events between dosing cohorts or to perform adequate Cochran-Armitage trend tests for dose-toxicity.

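### Section 10.1 attaches laboratory grading to an undefined judgement of clinical significance, which conflicts with its own adverse event definition and can only take Grade 2+ laboratory values out of the primary safety endpoint

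*Combined protocol and SAP*

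**What the plan says.** Four parts of the protocol bear on how a laboratory value becomes a graded safety outcome.

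- **Section 10.1, definition.** An adverse event is "any unfavorable and unintended sign (including an abnormal laboratory finding), symptom or disease temporally associated with the administration of an investigational product". No significance condition is attached. The section then states: "Adverse events will be described by duration (start and stop dates and times), severity, outcome, treatment and relation to study drug".
- **Section 10.1, AE Severity.** CTCAE version 3.0 "should be used to assess and grade AE severity, including laboratory abnormalities judged to be clinically significant". The working criteria are held elsewhere: "The modified criteria can be found in the study manual". Events that those criteria do not cover fall back on Table 1, which grades by discomfort, limitation of activity and need for intervention.
- **Synopsis, Primary Endpoint.** Safety and tolerability, with "no Grade 2 or greater clinical or laboratory adverse effects".
- **Section 14.3.** "Adverse events will be tabulated by dosing cohort and will include the number of participants for whom the event occurred", with rate, severity and relationship to study drug. It gives no Grade 2 threshold and no rule for laboratory values.

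Grades are also used for monitoring. The synopsis and section 10.4 act on a single drug-related Grade 4, or a pair of drug-related Grade 3s, whether adverse event or laboratory abnormality. The section 10.4 list includes "Two Grade 3 drug-related adverse event or laboratory abnormality". Section 13 holds enrolment on Grade 3 events possibly caused by the intervention and on any Grade 4 event.

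**The concern.** If every laboratory value were graded, there would be no reason to single out those judged clinically significant. The natural reading of the severity paragraph is therefore that a judgement comes before the grade. That does not fit with the definition a few lines earlier, and the endpoint and analysis sections do not settle which one governs. Two analysts holding the same data could report different primary safety results, and both could cite section 10.1.

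A significance condition also works in one direction. It can stop a value that meets the numeric limits for Grade 2 or higher from being counted, but it cannot create one. Any effect is towards a cleaner safety report, in a study whose primary objective is safety and whose first cohort is open label.

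**Working it through.** The plan states no event rate, power or precision for the laboratory part of the endpoint, so there is no figure to reproduce. The check is a comparison of text, followed by an illustration of sensitivity.

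**Step 1: the text side by side.**

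| Place | What decides whether a laboratory value counts |
|---|---|
| 10.1, definition | Any abnormal finding; severity recorded |
| 10.1, AE Severity | Graded if judged clinically significant; judge and criterion not given |
| Synopsis, Primary Endpoint | Grade 2 or higher; no mention of significance |
| 14.3 | Adverse events by severity; silent on laboratory values |
| Synopsis and 10.4 rules | Grade 3 or 4 and drug-related; no mention of significance |

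The first two rows conflict, and the remaining rows do not resolve the conflict. Elsewhere the protocol grades without such a judgement. Diarrhea in section 10.4 is graded mainly on stool counts, virologic failure is a copies/mL limit, and exclusion 6b uses Grade 2 liver tests with no significance condition. The Table 1 fallback does not help, because it describes symptoms and activity and cannot sensibly grade a symptomless laboratory value.

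**Step 2: how much data is involved.** From the Study Events Tables, post-dose blood counts in kansui phases are 5 per Cohort 1 participant (0.5, 2 and 4 hours, Day 2, Day 31). They are 10 per Cohort 2 participant (3 on the first dosing day, 1 on the second, 4 on the third, then the 24-hour and final visits). Metabolic panels are 2 and 4 respectively.

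- Blood counts: 2 × 5 + 6 × 10 = 70
- Metabolic panels: 2 × 2 + 6 × 4 = 28

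These are the sampling occasions. Only abnormal values among them could be affected, and the documents give no rate for those.

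**Step 3: sensitivity of a count out of 8.** Let p be the chance that a participant has a Grade 2+ laboratory value by the numeric limits, and s the chance that it is judged significant and so graded. Both are assumptions. Participants are taken as independent, with one judgement each.

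P(no participant counted) = (1 − p·s)^8

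| p | s = 1 | s = 0.75 | s = 0.5 | s = 0.25 |
|---|---|---|---|---|
| 0.1 | 0.43 | 0.54 | 0.66 | 0.82 |
| 0.2 | 0.17 | 0.27 | 0.43 | 0.66 |
| 0.3 | 0.06 | 0.13 | 0.27 | 0.54 |

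At p = 0.2, grading everything gives 0.8^8 = 0.17, and grading half gives 0.9^8 = 0.43. The second figure equals the result for p = 0.1 with everything graded. A clean report therefore cannot distinguish a low event rate from a selective grading step unless the step is defined. If a participant has several abnormal values, there are more chances for one to be graded, and the effect is smaller than shown.

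**The case against.** The strongest reply is that this is loose drafting. The severity sentence says that grading includes significant laboratory abnormalities; it does not say that other values go ungraded. The definition in the same section covers every abnormal finding. All laboratory values are reported within 48 hours (sections 10.3 and 13), and the team reviews laboratory abnormalities and their relation to treatment. The study manual may already specify numeric grading.

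Much of this stands, and it rules out several stronger readings that a reader might infer:

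- *That only significant values are graded, on the investigator's opinion.* The word only is not in the text and no judge is named. Section 10.1 contradicts itself; it does not set a clear exclusion.
- *That the endpoint flips from met to not met.* Section 14.3 tabulates and sets no pass/fail criterion. What can change is the reported count, for example from 1 of 8 to 0 of 8 if no other Grade 2+ event occurs.
- *That the pause rules can be bypassed.* Those rules name laboratory abnormalities separately from adverse events and already require a judgement of drug-relatedness. The virologic rule is numeric. Section 13 lists laboratory data among the regular administrative reports, and the Safety Monitoring Committee may stop the study for any safety concern.
- *That staff bias is shown.* Kansui's cathartic effect could reveal treatment in Cohort 2, but nothing in the documents links that to how laboratory values are judged.

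What the reply does not answer is the grading itself. Reporting and team review show that values are seen, not that each receives a grade. The committee's review in section 10.4 is described in terms of adverse event summaries, CD4+ counts and HIV RNA, so an ungraded value may not reach it as a countable grade.

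**Conclusion.** The concern holds as an internal conflict with a one-sided consequence. Section 10.1 ties laboratory grading to an undefined judgement, contradicts its own definition, and leaves unclear which laboratory values enter the primary safety endpoint. Read as written, the condition can only lower the count of Grade 2+ laboratory events, and among 8 participants one value is enough to change what is reported.

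The size cannot be estimated from the documents. The probabilities above rest on assumed values of p and s and show only that the result is sensitive to the step. The conclusion also assumes that the study manual does not already require numeric grading of all values; if it does, the protocol need only say so. This is a worthwhile, low-cost improvement. It does not show that the safety monitoring fails.

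**What to change.** For the primary safety analysis, change two places.

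1. **Section 10.1:** state that every post-baseline laboratory value is graded by the numeric CTCAE criteria. Record clinical significance as a separate field that does not affect the grade.
2. **Section 14.3:** tabulate each participant's worst post-baseline laboratory grade and the shift from baseline, by treatment phase so that Cohort 2 placebo and kansui periods are shown apart. Count towards the endpoint only grades that are new or worse than baseline.

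For the pause and stop rules in the synopsis and section 10.4, and the enrolment hold in section 13, reconcile these sections with section 10.1 by stating whether the clinical-significance wording applies to them. Which way that is decided is a clinical matter for the investigators and the Safety Monitoring Committee.

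The cost is a few sentences and a short programmed grading step on data already collected. Some trivial values will be listed, and the safety summary may look slightly less favourable.

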10.2 Serious Adverse Experiences (SAE)

An SAE is defined as any AE occurring at any dose that results in any of the following outcomes:

- death
- a life-threatening adverse experience
- inpatient hospitalization or prolongation of existing hospitalization
- a persistent or significant disability/incapacity

- a congenital anomaly/birth defect

Other important medical events may also be considered an SAE when, based on appropriate medical judgment, they jeopardize the participant or require intervention to prevent one of the outcomes listed.

10.2.1 Serious Adverse Experience Reporting

The study site will document all SAEs that occur (whether or not related to study drug) per the University of Utah IRB Guidelines. The collection period for all SAEs will begin after informed consent is obtained and end after procedures for the final study visit have been completed.

In accordance with the standard operating procedures and policies of the local Institutional Review Board (IRB), the site investigator will report SAEs to the IRB.

10.3 Monitoring

During the study, safety will be monitored by a Safety Monitoring Committee (SMC), which will be led by a qualified University of Utah faculty member in the Department of Medicine with expertise in HIV clinical research (see Section 13 below). The SMC will review all study procedures before the initiation of the study. They will have the full and final authority to stop the study for any safety concern at any point. The Principal Investigator at the University of Utah will be the primary medical monitor responsible for study adverse event monitoring and will report adverse events and unanticipated problems to the University of Utah IRB and the SMC. All participants will be followed for possible adverse events and unanticipated problems throughout the study period.

Participants will be monitored in an outpatient clinic during the first 4-6 hours post-dose on dosing days. At each visit, participants will be assessed for any new symptoms, and a study coordinator will obtain vital signs. The study will require 48-hour reporting of all laboratory values, signs/symptoms, and serious adverse events (SAEs). The study will have intensive Phase I safety monitoring, which will include regular and frequent team review (every week for the first 2 months of the study; then every two weeks thereafter) of all reported events. In addition, for any Grade 3 or 4 events, sites will be instructed to contact the study team by email.

- Grade 1 or 2 Toxicity: Participants who develop a Grade 1 or 2 AE or toxicity may continue study treatment. If a participant chooses to discontinue study treatment, the site should notify the kansui protocol core team as noted above, and encourage the participant to complete any remaining study visits.
- Grade 3 or 4 Toxicity: Participants experiencing Grade 3 or 4 AEs requiring permanent discontinuation of study treatment should be followed closely for resolution of the AE to Grade ≤ 2 and the protocol core team must be notified. Participants discontinuing study treatment should be encouraged to complete any remaining study visits.

[name] will be contacted directly to report medical concerns or questions regarding safety.

[contact]

